10.4. Population for Analyses

Statistical analyses will be based on a per protocol analysis - i.e., performed only on the SSS scores for subjects that have completed the full 8 week treatment period.

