Demonstrate high subject compliance.	Diary wear time responses. Number of dropouts due to non-compliance.	Compliance is measured by adherence to daily wear and actual vs advised wear time.
Obtain user feedback on the comfort, use, and design of the study device.	User Feedback Survey responses at the end of Treatment Period	Collects qualitative data on practical aspects of the device.

5. Study Design

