7.3. Treatment Period

The Treatment Period begins the first day that the subject begins wearing the device. Electronic Diaries are sent to subjects every day from the first day of treatment for 56 days. Subjects should be reminded if (s)he does not complete an entry. If 3 or more consecutive diary entries are missed, the site should contact the subject to remind them to complete entries or they could be withdrawn from the study. No more than 3 consecutive Diary entries and no more than 25% of total entries should be missed (14 out of 56 diary entries), but withdrawal due to missed Diary entries will be up to Sponsor after evaluating the situation

Follow-up surveys are electronically sent to subjects every 2 weeks from the subject's first day of device wear up to 8 weeks. The subject should complete the surveys within 3 days and reminders should be sent if the subject does not complete the survey. If the subject does not complete the survey within 3 days, the site should follow up with the subject to remind them to complete the survey and address any issues preventing the subject from completing the survey. All subject correspondences and contact attempts should be documented.

On the last day of treatment, the subject will complete a User Feedback Survey. This should be completed within 5 days.

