7.7. Subject Withdrawal

Potential reasons for withdrawal or removal of subjects are outlined below:

- Subject decides it is in his/her best interest to withdraw
- Principal investigator decides it is in the subject's best interest to withdraw
- Subject is noncompliant during the 12-week treatment period (i.e., Sponsor deems subject has missed too many Diary entries or Follow-ups).
- Subject is lost-to-follow-up at any point (more than 5 documented attempts to contact and ask to complete follow-ups with no response after 3 weeks)
- Subject fails to refrain from other CTS treatments or therapies.

If the subject is withdrawn, the PI or designated staff member must fill out the Exit Form and document the reason for withdrawal or removal of the subject from the study. Unless the subject requests removal of their data, any data or information collected from the subject will remain in the database and analyzed at the sponsor's discretion.

8. Study Supplies

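### Every SSS analysis is restricted to 8-week completers, with no all-randomised analysis and no missing-data method despite 25% expected attrition; Section 7.7 blurs what happens to SSS from subjects withdrawn before week 8

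*Combined protocol and SAP*

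**What the plan says.** Section 10.4 sets one population for efficacy, labelled per protocol: analyses are "performed only on the SSS scores for subjects that have completed the full 8 week treatment period". Section 10.5 then lists a paired one-sided t-test for the primary endpoint (active arm, week 8 against baseline), a two-sample one-sided t-test for the secondary endpoint, a repeated-measures analysis of variance, and descriptive methods for the exploratory endpoints. It widens the population for safety only. It names no imputation, no likelihood-based method and no sensitivity analysis.

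Section 10.2 assumes 25% attrition and uses it to enlarge the sample. Section 7.7 lists potential withdrawal reasons, among them the subject's own decision, "Subject fails to refrain from other CTS treatments or therapies", and noncompliance where the "Sponsor deems subject has missed too many Diary entries or Follow-ups". Section 7.3 gives diary limits but adds that "withdrawal due to missed Diary entries will be up to Sponsor after evaluating the situation". Section 9.3 foresees adverse events that end device use.

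For withdrawn subjects, Section 7.7 states that, unless the subject asks for removal, "any data or information collected from the subject will remain in the database and analyzed at the sponsor's discretion".

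**The concern.** A subject whose symptoms persist may turn to another therapy, decide to stop, or let the diaries lapse. Each route can lead to withdrawal before week 8 and so out of every SSS analysis. The completers are then a group selected partly by outcome, in a trial that the synopsis calls confirmatory/pivotal.

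The two tests are exposed differently. The primary test uses the active arm alone, so neither blinding nor equal drop-out in the two arms protects it: if active drop-outs do worse than completers, the completer mean overstates the change. The between-arm test is distorted when drop-out, or its link with response, differs by arm, and the distortion can go either way.

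Section 7.7 adds a smaller difficulty. Its discretion clause does not fit the word only in Section 10.4 as regards SSS from subjects withdrawn before week 8. It is no conflict for diary or safety data, for the Section 4 endpoint "Number of dropouts due to non-compliance", or for subjects withdrawn after week 8, who are in the Section 10.4 set.

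**Working it through.** **Inputs.** From Section 10.2: 51 per arm, SD 0.7, difference 0.4, one-sided 0.05, power 0.8, attrition 25%. The pilot drop-out is printed there as 20% (2 of 13), but 2/13 = 15.4%. I therefore used 13, 10 and 8 of 51 lost (25%, 20%, 15.4%). The link between drop-out and outcome is an assumption, because the documents give none.

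**The plan's own figure.** By the normal approximation, 2 × (1.645 + 0.842)² × 0.7² / 0.4² = 37.9, so 38 completers per arm; 38 / 0.75 = 50.7, so 51 per arm and 102 in total. The stated sample size reproduces. It is built to give about 80% power on completers alone (0.795 by noncentral t with 38 per arm).

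**Simple bound.** Completer mean minus all-randomised mean = (fraction lost) × (completer mean − drop-out mean). At 25% lost, a gap of 0.4 gives 0.10 and a gap of 0.8 gives 0.20, that is, a quarter to a half of the 0.4 target.

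**Selection model.** Drop the k of 51 subjects lowest on a latent score that has correlation r with week-8 improvement. With p = k/51, bias ≈ r × 0.7 × φ(z_p)/(1 − p).
- k = 13: φ/(1 − p) = 0.321/0.745 = 0.431, so the bias is 0.09 / 0.15 / 0.21 for r = 0.3 / 0.5 / 0.7.
- k = 8: 0.240/0.843 = 0.285, so the bias is 0.06 / 0.10 / 0.14.

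Simulated rejection rates of the nominal one-sided 5% tests, with no true effect:

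| Test and drop-out pattern | 13 of 51 lost | 8 of 51 lost |
|---|---|---|
| Primary, active drop-outs worse | 20% / 39% / 64% | 14% / 25% / 40% |
| Between-arm, only active drop-out informative | 14% / 24% / 39% | 11% / 16% / 25% |
| Between-arm, both arms alike | 5% / 6% / 7% | 5% / 6% / 6% |
| Between-arm, only sham drop-out informative | 1.5% / 0.6% / 0.2% | 2.2% / 1.2% / 0.6% |
| Between-arm, active drop-outs worse and sham better | 30% / 61% / 88% | 20% / 39% / 62% |

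With 10 of 51 lost, the primary test rejects 16% / 31% / 51%. If active drop-outs do better than completers, the mean is deflated by the same amounts and the primary test rejects under 2%.

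**Tipping points when completers show 0.4.** The result is lost when 0.4 − p × gap falls below t × SE, with SE taken on completers or on all 51.
- 13 lost, within arm: thresholds 0.192 and 0.164, so gap = (0.4 − 0.192)/0.255 = 0.82 to (0.4 − 0.164)/0.255 = 0.92.
- 13 lost, between arms, active drop-outs alone worse: thresholds 0.267 and 0.230, so gap = 0.52 to 0.67.
- 8 lost: 1.41 to 1.50 within arm and 0.95 to 1.08 between arms.

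**How far a mixed model helps.** Assume a large sample, drop-outs observed to week 4, and a correlation of 0.70 between week-4 and week-8 scores. The bias left at 13 lost is then 0.05 / 0.08 / 0.12, and 51–58% of the completer bias remains. If half of the drop-outs also return the week-8 survey, it falls to 0.02 / 0.03 / 0.05.

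**The case against.** The strongest reply is that the rejection rates assume no true change, while Section 3.3.2 itself expects a possible placebo response. An uncontrolled paired test may reject for that reason alone, so 64% is not a realistic false-positive rate due to completer selection. This stands: the rates show sensitivity to selection and are not forecasts.

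It is also fair that a completer change of 0.4 is fairly robust. At 13 lost, r = 0.3 / 0.5 / 0.7 implies gaps of about 0.35 / 0.58 / 0.82, so the primary result survives the first two and is borderline at the third. At 8 lost, the r = 0.7 gap is about 0.87, below both tipping points. The between-arm result at 13 lost is the fragile one. But the plan has no analysis that would demonstrate robustness in the actual data.

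Mitigating text exists. The Sponsor's clinical research team is blind to allocation (Section 10.3), diary limits, reminders and site contact are specified (Section 7.3), loss to follow-up requires more than five documented contact attempts (Section 7.7), and the later offer of the active device should help keep sham subjects (Section 6.6). The 25% also covers follow-up, so losses before week 8 may be fewer. These points limit selective or heavy drop-out; they do not stop subjects leaving because of how they respond.

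Finally, Section 7.7 can be read as a data-retention sentence, with Section 10.4 as the specific rule. That is reasonable, and one clarifying sentence would settle it.

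**Conclusion.** The concern holds and should be fixed before analysis. Completer-only efficacy is a stated rule, not an omitted detail, and it governs both the primary and the secondary result. The sample size is arithmetically sound, but its attrition allowance addresses precision only.

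The size of the bias cannot be known from the documents. Under the assumed correlations of 0.3 to 0.7 it is 0.06 to 0.21 points in the active-arm mean for 8 to 13 of 51 lost, against a target of 0.4, and the direction could be reversed. Which test suffers more depends on the mechanism. If both arms behave alike, only the one-arm test is materially biased; if they differ in opposite directions, the between-arm test is worse, although the documents give no particular reason to expect that pattern. The Section 7.7 inconsistency is confined to SSS from subjects withdrawn before week 8.

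**What to change.** 1. In Sections 10.4 and 10.5, make the main efficacy analysis all randomised subjects, as randomised, using every available SSS at baseline and weeks 2, 4, 6 and 8 under one prespecified method, for example a repeated-measures mixed model with baseline SSS. Report the week-8 active-arm change (primary) and the week-8 active-minus-sham difference (secondary).
2. Keep sending the existing surveys through week 8 to consenting subjects who stop the device. This recovers more than the model does, and scores that are not collected cannot be recovered later. State in advance how scores after other CTS therapy are handled in each analysis; if the rule differs between the two contrasts, specify two fits.
3. Because a mixed model assumes data missing at random, add a prespecified sensitivity analysis, such as a delta-adjusted tipping point in the active arm alone and in both arms.
4. Keep the completer analysis as supportive.
5. In Section 7.7, state that SSS collected before withdrawal enters the prespecified efficacy analysis and is not left to discretion.

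The cost is low to moderate: protocol text, consent wording, continued survey contact and modest extra analysis. Section 7.3 already has it that "Follow-up surveys are electronically sent to subjects every 2 weeks", and Section 10.5 already plans a repeated-measures analysis.

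The price is possible dilution. If 25% drop out and gain all, half or none of a 0.4 benefit, the all-randomised difference is 0.40, 0.35 or 0.30. Between-arm power with 51 per arm is then 0.889, 0.806 or 0.693, against 0.795 for 38 completers (0.837 for 43) at 0.4. The 51-per-arm figures are upper bounds, since they require a week-8 SSS from everyone.

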10.5. Statistical Analyses

The primary efficacy endpoint is the improvement (reduction) in SSS of the treatment group at 8 weeks after the first day of device wear. The primary efficacy endpoint will be analyzed using a paired, one-sided t-test.

The secondary efficacy endpoint is the improvement (reduction) in SSS of the treatment group compared to the sham group at T4 (8 weeks after the first day of device wear). The secondary endpoint will be analyzed using a two sample one-sided t-test.

A repeated measures analysis of variance will be used to evaluate changes over time in both the active and sham groups.

The exploratory endpoints will be analyzed using descriptive methods.

Safety analyses will be performed on all subjects that received treatment.

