2.1. Study Synopsis

Title	Randomized Controlled Clinical Trial of Non-invasive Device to Alleviate Symptoms of Carpal Tunnel Syndrome
Study Description	Sham-controlled, multi-center and remote patient-centered randomized controlled clinical trial to investigate the efficacy of a novel non-invasive, unobtrusive study device in reducing symptoms of carpal tunnel syndrome (CTS). Daily wear of the study device is expected to significantly reduce symptom severity (evaluated by the Boston Carpal Tunnel Questionnaire) in mild to severe CTS-diagnosed patients. Subjects are randomized into the active device group or sham group for 8 weeks, then followed for 12 weeks post-treatment.
Objectives	Primary: Investigate whether daily wear of the study device significantly reduces patient-reported CTS symptom severity. Secondary: Determine whether there is a difference between the active device group and sham group. Investigate whether changes in symptoms are sustained or continue post-treatment.
Endpoints	Primary: BCTQ-SSS of the treatment group at 8 weeks compared to Baseline. Secondary: BCTQ-SSS at 8 weeks and at post-treatment timepoints between the treatment and sham groups
Study Population	Sample size: 102 (51 in each arm) Adults diagnosed with mild to severe CTS, ages 21-65 of any gender Any geographic location within the United States
Phase	Confirmatory/pivotal
Sites	At least 3 physical sites located in the United States (national enrollment)
Study Device	Stiffness-optimized thermoplastic curved band that has a strong biocompatible adhesive in the center of the concave side of the device. Device is designed to decompress the median nerve and thus relieve symptoms of carpal tunnel syndrome.
Study Duration	Approximately 12 months
Participant Duration	5 months

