3.3.2. Known Potential Benefits

Prolonged wear (anywhere from 1 week to 4 weeks) of the study device may reduce symptoms of CTS.⁹

The sham device may cause a placebo effect and reduce symptoms of CTS as well.

4. Objectives & Endpoints

Objective	Endpoints	Explanation
Primary		
Investigate whether daily wear of the study device significantly reduces patient-reported CTS symptom severity.	Symptom Severity Score (SSS) of the Boston Carpal Tunnel Questionnaire (BCTQ) in the treatment group at 8 weeks compared to Baseline.	The SSS is a validated combined measure of the patient's perception of the level and frequency of pain, numbness, tingling caused by CTS. 8 weeks is the end of the treatment period.
Secondary		
Determine whether there is a difference between the active device group and sham group.	Comparing SSS at 8 weeks and between the active device group and sham group.	Between group comparison conducted for the primary outcome variable at the primary endpoint (8 weeks).

Additionally, we will determine if this difference continues post-treatment.	Comparing SSS 1 month post-treatment (12 weeks) between the active device group and sham group.	Single timepoint at 12 weeks compared between groups for post-treatment analysis.
Exploratory		
Does CTS symptom improvement occur before 8 weeks?	Significant reduction in SSS compared to Baseline at any time point before 8 weeks.	Identification of significant SSS reduction before 8 weeks suggests a shorter minimum duration of wear.
Do unilateral and bilateral CTS patients respond differently to treatment?	Change in SSS at 4 and 8 weeks in a unilateral subgroup compared to a bilateral subgroup.	Unilateral patients showed significant SSS improvement in the pilot study, whereas bilateral patients seemed to show none. ⁹ Both 4- and 8-week timepoints compared in case a difference is seen before the end of treatment.
Do patients respond differently based on Baseline severity?	Change in SSS at 4 and 8 weeks in mild, moderate, and severe subgroups.	AANEM guidelines categorize CTS into 3 severity groups.
Describe the effect of study device treatment on patients with hormonal-induced CTS, such as pregnancy.	Change in SSS at or within 8 weeks in a subgroup of pregnant women.	The study device is hypothesized to work primarily for repetitive stress induced CTS. Pregnant women often develop CTS due to swelling of the tissue.

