10.1.2. Secondary Efficacy Endpoint

H₀: Daily wear of the study device does not improve symptom severity in comparison to sham treatment.

H₁: Daily wear of the study device improves symptom severity by at least 0.4 points more than the sham group.

H₀: Changes in symptom severity are not sustained after stopping treatment.

H₁: Changes in symptom severity are sustained or continue after stopping treatment.

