10.2. Sample Size Determination

A total of 102 subjects are required for this study, with 51 in each group.

The outcome measure used for calculations in the SSS of the BCTQ, which ranges from 1 to 5 with 1 being no symptoms (improved) and 5 being the worst symptoms (worsened).

A moderate effect size of 0.4 was chosen, assuming that study device efficacy is 0.4 greater than sham.

The pilot study experienced a drop-out rate of 20% (2 out of 13 total). With the longer treatment and follow-up times of this study, a higher drop-out is expected. Therefore the sample size calculation is modified by an estimated attrition rate of 25%.

The primary objective examines the 8 week vs baseline within-active group SSS change. Sample size determination explanation. The power analysis using the above results in a significance level of 0.05 and a power of 0.94*.

The secondary objective examines the change in SSS after 8 weeks between the active study device and sham groups. Sample size calculation is based on a parallel, one-sided t-test power analysis to identify an effect size of 0.4, standard deviation of 0.7 (based on the pilot study PPS-CTMD-15-001), significance level of 0.05, power of 0.8, and an estimated attrition rate of 25%.

The sample size was chosen to meet both the primary and secondary objectives.

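### The primary endpoint of this sham-controlled pivotal trial is the active arm's change from its own baseline, so it can be met by a device no better than sham.

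*Combined protocol and SAP*

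**What the plan says.** The synopsis (section 2.1) describes a "Sham-controlled, multi-center and remote patient-centered randomized controlled clinical trial" and gives its phase as confirmatory or pivotal. The same synopsis sets the primary endpoint as "BCTQ-SSS of the treatment group at 8 weeks compared to Baseline". The objectives table in section 4 agrees: "Symptom Severity Score (SSS) of the Boston Carpal Tunnel Questionnaire (BCTQ) in the treatment group at 8 weeks compared to Baseline". The primary null hypothesis in section 10.1.1 is that wearing the device brings no improvement, with no reference to sham. Section 10.2 describes the primary objective as a within-active-group change and gives it a power of 0.94. Section 10.5 states the test: "The primary efficacy endpoint will be analyzed using a paired, one-sided t-test".

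The randomised comparison is secondary wherever it appears. Its alternative hypothesis in section 10.1.2 is "Daily wear of the study device improves symptom severity by at least 0.4 points more than the sham group", and section 10.5 assigns it a one-sided two-sample t-test.

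Two other statements matter here. Section 3.3.2 says "The sham device may cause a placebo effect and reduce symptoms of CTS as well". Section 6.1 requires an SSS of at least 2 at entry, on the same scale that is later the outcome.

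**The concern.** A change from baseline in one arm adds together the device effect, the placebo response, the natural course of the condition and regression to the mean. A paired test against zero cannot separate them. The sham arm was included to do so, but it plays no part in the primary test. Randomisation, sham and blinding therefore contribute nothing to the primary conclusion.

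The planning value has the same problem. Section 10.2 introduces it with "A moderate effect size of 0.4 was chosen, assuming that study device efficacy is 0.4 greater than sham", which is a between-group quantity. It then says that the primary power follows from the inputs above it, and that power is for a within-arm test. However the 0.94 was derived, it is the chance of detecting a change from baseline. It is not the chance of detecting an effect of the device.

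At stake is what the main result means. The trial could be reported as positive on its primary endpoint while the sham arm improved just as much.

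**Working it through.** **Inputs from the documents.** 51 per arm, attrition 25%, difference 0.4, SD 0.7, one-sided alpha 0.05, power 0.80 for the sham comparison (section 10.2); completers only (section 10.4); entry SSS of at least 2 (section 6.1).

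**Assumed, because the documents do not give it.** A non-specific improvement *d* common to both arms, from 0.0 to 0.5 points. The SD of change is taken as 0.7 in each arm.

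**1. Reproduce the plan's sample size.** Per arm: 2 × (1.645 + 0.842)² × (0.7/0.4)² = 37.9, rounded up to 38. Allowing for attrition: 38/0.75 = 50.7, rounded up to 51 per arm, 102 in total. This matches, so the sample size comes from the sham comparison.

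**2. Smallest significant result, 38 completers per arm (51 × 0.75 = 38.25).**
- Within the active arm: t(0.95; 37) × 0.7/√38 = 0.192 points.
- Between arms: t(0.95; 74) × 0.7 × √(2/38) = 0.267 points.

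**3. Probability that the primary test is positive when the device equals sham.** Paired one-sided test, noncentral t with 37 degrees of freedom and noncentrality *d*/(0.7/√38). The last column comes from 50,000 simulated trials per row, with both tests applied to the same data.

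| Shared change *d* | P(primary positive) | P(primary positive, sham comparison negative) |
|---|---|---|
| 0.0 | 0.05 | not run |
| 0.1 | 0.22 | not run |
| 0.2 | 0.53 | 0.49 |
| 0.3 | 0.83 | 0.78 |
| 0.4 | 0.965 | 0.92 |
| 0.5 | 0.996 | not run |

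In the simulated rows the sham comparison was positive in about 5% of trials, as it should be.

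**4. Regression to the mean from the entry cut.** The expected fall is (1 − reliability) × SD × φ(z)/(1 − Φ(z)), with z = (2 − mean)/SD. Assume a population SD of 0.7, a mean of 2.2 to 3.0 and a reliability of 0.7 to 0.9.
- Largest case (mean 2.2, reliability 0.7): 0.3 × 0.7 × 0.625 = 0.13 points.
- Smallest case (mean 3.0, reliability 0.9): 0.1 × 0.7 × 0.156 = 0.01 points.

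This is below the 0.192 threshold on its own, but it adds to any placebo response and natural improvement.

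**5. Power after the change.** Difference 0.4, SD 0.7, 38 completers per arm, one-sided 0.05: 0.801 by the normal approximation and 0.795 by the t-test.

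**Side check on 0.94.** With 0.4, SD 0.7 and 38 completers, the planned one-sided paired test has power 0.965 (t) or 0.970 (normal). The derivation of 0.94 is not shown, and nothing in this point depends on it.

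**The case against.** The strongest reply is that the controlled question has not been neglected. Superiority to sham is hypothesised in section 5.1, specified in section 10.1.2 and powered at about 80%, and section 10.2 says that the sample size serves both objectives. The documents give no trial-level rule for success, so a reader would see both results. This is correct, and it limits the claim: what can happen is that the primary endpoint is met. It does not remove the problem, because the plan ranks the uncontrolled result first and nothing makes the conclusion depend on the sham comparison.

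The probabilities also rest on an assumed sham response. That is true, and the range starts at zero for that reason. The direction needs no particular value: any shared improvement above zero raises the chance of a positive primary test above 5%.

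It is also fair to say that section 10.1.1 gives 0.4 as the within-arm alternative, so that figure is not used solely as a margin over sham. The within-arm power still does not describe a device effect.

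Finally, requiring both tests to succeed would also close the gap. It would, but making the sham comparison primary is simpler. The completers-only population and the choice of a one-sided test are separate matters. They affect the sham comparison too, and changing the primary endpoint does not settle them.

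**Conclusion.** The concern holds and should be corrected before unblinding. Sections 2.1, 4, 10.1.1, 10.2 and 10.5 agree on a within-arm primary endpoint, so no other section repairs it. With a device equal to sham, an SD of change of 0.7 and 38 completers in the active arm, the primary endpoint is met with probability 0.53 to 0.965 for shared improvements of 0.2 to 0.4 points. An observed fall of 0.19 points is enough. These probabilities depend on the assumed shared improvement and SD. That the primary test cannot distinguish device from sham follows from the design alone.

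**What to change.** In sections 2.1, 4, 10.1, 10.2 and 10.5:

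- Make the active-versus-sham difference in SSS change at Week 8 the primary endpoint. Report the within-active change as descriptive or supportive.
- State the alternative as a difference greater than zero, and keep 0.4 as the planning value. The planned test is against zero and becomes significant at an observed difference of about 0.27, so it cannot establish a benefit of at least 0.4.
- Test the Week 12 difference only if the Week 8 difference is significant.

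The cost is wording, with no extra subjects or data. Stated primary power falls from 0.94 to about 0.80 (0.795 by the t-test). Keeping 102 subjects relies on the plan's one-sided 0.05 test. If the sponsor chose a two-sided 0.05 test instead, 51 per arm would give about 69% power, and 80% would need 132 subjects (normal approximation) or 134 (t-test).

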7.2. Enrollment, Baseline Assessment, and Randomization

7.2.1. Enrollment Procedures

After the subject has passed the pre-screening questionnaire, the subject will begin enrollment, which includes reading and signing the ICF/HIPAA Authorization, completing the Enrollment Form which includes the BCTQ and NPRS, and confirmation of CTS diagnosis via NCS. After confirming meeting all inclusion/exclusion criteria, the subject is considered enrolled. The subject will be randomized into either the active device group or the sham group and assigned a Subject ID.

Once the subject is enrolled, study devices are shipped (expedited) to the subject to begin treatment as soon after enrollment as possible. If a subject is bilateral, only the worse wrist (via NCS severity and/or SSS score) will be treated during the study. If NCS severity and/or SSS score are the same for both wrists, the dominant wrist will be treated. Standardized training and instructional materials will be provided to the subject on how to use the study devices, how and when to complete surveys, Diaries, etc.; how and when to report AE's/SAE's; and how to contact site staff or PI.

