7.2.3. Baseline Assessment

The Enrollment CRF captures Baseline assessment measures. These include:

- Date of birth/age
- Gender
- CTS severity (mild, moderate, or severe, from NCS)
- CTS diagnosis by hand (unilateral/bilateral, right/left/both)
- BCTQ and NPRS for affected hand(s)

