10.3. Randomization and Blinding Procedures

A simple randomization scheme is used to allocate subjects into the treatment group or the sham group. Site staff will be blinded to the randomization list and the Sponsor clinical research team blind to the allocation of each subject.

Blinding will be broken for each sham group participant at his/her first post-treatment follow-up (Week 12) so that the site can offer the sham group participant the opportunity to try the active study device. Complete blinding will be broken at the end of the study when all data has been entered and validated and the database has been locked.

Blinding may be broken if a subject experiences a SAE and if knowledge of the device is necessary for proper medical treatment of the SAE. Due to the low risk and minimal side effects associated with the device from previous studies, unblinding in most cases is not deemed necessary for medical treatment.

The subject's assigned site must obtain approval from the Sponsor to break the blind. After approval, the Shipping Associate responsible for randomization will provide the assignment for the subject in question. After a subject's treatment has been revealed, this must be noted along with reasons for breaking the blind in the subject's records and in the Deviation/Violation Log.

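### The active-versus-sham test is an unadjusted t-test; adding baseline SSS as a covariate costs almost nothing and may add power, by an amount the documents cannot fix

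*Combined protocol and SAP*

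**What the plan says.** Section 10.5 of the combined protocol and SAP defines the secondary endpoint as the reduction in SSS in the active group compared with sham at Week 8, and continues: "The secondary endpoint will be analyzed using a two sample one-sided t-test". No covariate is named. The next sentence adds a second analysis: "A repeated measures analysis of variance will be used to evaluate changes over time in both the active and sham groups". That analysis is not designated as the test of the secondary endpoint, and it names no baseline covariate either.

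The baseline value is available. Under Section 7.2.1, enrollment includes "completing the Enrollment Form which includes the BCTQ and NPRS, and confirmation of CTS diagnosis via NCS", and the subject is randomized only after eligibility is confirmed. Section 6.1 requires an SSS of at least 2 at entry. Section 10.3 says: "A simple randomization scheme is used to allocate subjects into the treatment group or the sham group". Nothing in the allocation therefore balances baseline SSS between arms.

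The documents describe the compared variable in two ways. The synopsis (Section 2.1) has "Secondary: BCTQ-SSS at 8 weeks and at post-treatment timepoints between the treatment and sham groups", and the objectives table in Section 4 has "Comparing SSS at 8 weeks and between the active device group and sham group"; both read as the score itself. Sections 10.2 and 10.5 refer to a change or reduction, and the alternative hypothesis in Section 10.1.2 is that the device "improves symptom severity by at least 0.4 points more than the sham group".

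**The concern.** The primary endpoint is a within-arm change from baseline. The secondary comparison is therefore the efficacy test that separates a device effect from the placebo response that Section 3.3.2 itself anticipates. It is also the comparison for which Section 10.2 gives a full sample size calculation, with a power target of 0.80.

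If the test is run on change scores, baseline enters only by subtraction, which fixes its slope at 1. When the true slope is below 1, subtraction over-corrects: it adds noise and carries part of any chance baseline imbalance into the treatment estimate. ANCOVA estimates the slope. In a randomized comparison it is asymptotically never less precise than the change-score test, apart from about one degree of freedom. What is at stake is power at the same sample size, not validity.

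**Working it through.** **Inputs.** Section 10.2 gives a difference of 0.4, SD 0.7, one-sided 0.05, power 0.80, attrition 25%, and 51 per arm. The SD of 0.7 is attributed to the pilot. Section 5.2 reports a pilot SD of change from baseline of 0.68 at 4 weeks, so 0.7 is read as an SD of change.

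**The plan's own figure.** Normal approximation: n per arm = 2 × (1.645 + 0.842)² × 0.7² / 0.4² = 37.9, rounded up to 38. Then 38 / 0.75 = 50.7, rounded up to 51 per arm, 102 in total. This matches the plan. With 38 completers per arm, power is 0.801 by the normal approximation and 0.795 by the noncentral t (74 df).

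**ANCOVA at the same sample size.** Let s0 and s1 be the baseline and Week 8 SDs and ρ their correlation.

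- Variance of change = s0² + s1² − 2ρ·s0·s1, held at 0.7² = 0.49.
- ANCOVA residual variance = s1²(1 − ρ²).
- Proportional saving against the change score = (s0 − ρ·s1)² / 0.49.

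Worked example, s0 = s1 and ρ = 0.5: s1 = 0.7, residual variance = 0.49 × 0.75 = 0.3675, saving 25%, residual SD 0.606, power 0.886 (73 df).

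Neither ρ nor the SD ratio s0/s1 is in the documents, so both are assumptions. Saving and power:

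| s0/s1 | ρ = 0.3 | ρ = 0.5 | ρ = 0.7 |
|---|---|---|---|
| 0.75 | 18%, 0.861 | 8%, 0.822 | 0.5%, 0.796 |
| 1.00 | 35%, 0.922 | 25%, 0.886 | 15%, 0.849 |
| 1.25 | 50%, 0.967 | 43%, 0.947 | 37%, 0.929 |

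The comparator is 0.795 in every cell. Simulation with 20,000 replicates, including chance baseline imbalance, gave 0.790 to 0.799 for the change score and, for ANCOVA, values within 0.01 of the table. In the cell with ratio 0.75 and ρ = 0.7, simulated ANCOVA power was 0.791, so there is no gain there. Simulated type I error was 0.047 to 0.052 for the t-test and 0.048 to 0.054 for ANCOVA.

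**Effect of the entry rule.** Requiring SSS of at least 2 truncates baseline only, which favours a ratio below 1. Simulation used assumed pre-selection means of 2.3 to 3.0, SD 0.7 at both times and pre-selection ρ of 0.3 to 0.7, keeping subjects with baseline of at least 2. It gave SD ratios of 0.70 to 0.93 and savings of 7.5% to 29%. Applying those savings to an SD of change held at 0.7 gives power of about 0.82 to 0.90.

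**Cost if baseline is uninformative.** With zero saving, moving from 74 to 73 df changes power from 0.7948 to 0.7947.

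**Effect of imbalance, for illustration.** With both SDs 0.7, ρ = 0.5 and 38 per arm, the between-arm baseline difference has SD 0.7 × √(2/38) = 0.16. A one-SD imbalance shifts the change-score estimate by (1 − 0.5) × 0.16 = 0.08, which is 20% of the 0.4 target.

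**The case against.** The strongest reply is that nothing is wrong. The t-test is valid, the 102 reproduces exactly for it, and 0.80 is the plan's own target. Baseline already enters through the change score, so the real step is only from change score to ANCOVA, on a secondary endpoint. All of that stands, and it is why this is a suggestion and not a correction.

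The size of the gain has no documentary basis. That also stands. The row with ratio 1.25 needs baseline to be more variable than Week 8, which the entry rule makes less likely, so its figures should not be read as expected values.

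The entry-rule power figures are rescaled to an SD of change of 0.7. The simulated populations have their own SDs of change: about 0.75 to 0.79 at pre-selection ρ = 0.3 and 0.52 to 0.53 at ρ = 0.7. Without rescaling, power goes from about 0.70 to 0.75 up to 0.83 at ρ = 0.3, but only from about 0.95 to 0.965 at ρ = 0.7. Pre-selection ρ is also not the ρ of the table: 0.7 falls to about 0.56 to 0.65 after truncation. These points qualify the illustrated size. They do not reverse the direction.

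Finally, Section 10.4 restricts the analysis to subjects who complete the 8 weeks. The precision argument assumes comparable randomized groups, and baseline adjustment does not repair that restriction.

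**Conclusion.** The point holds as an efficiency improvement worth considering. The designated active-versus-sham test uses no baseline covariate, the covariate is collected before randomization on every eligible subject, and the cost of using it is about one degree of freedom.

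Against planned power of 0.795, ANCOVA gives 0.85 to 0.92 under equal SDs and ρ of 0.3 to 0.7, and about 0.82 to 0.90 under the entry-rule simulation with the SD of change held at 0.7. At ratio 0.75 and ρ = 0.7 there is essentially no gain. All these figures assume 38 completers per arm and rest on correlations and SD ratios that the documents do not supply. Confidence in the direction is good; confidence in the size is low.

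The difference in wording between Sections 2.1 and 4 and Section 10 is editorial. The operative text and the planning SD both point to change.

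**What to change.** In Section 10.5, replace the two-sample t-test with ANCOVA of Week 8 SSS on arm with baseline SSS as covariate, or the equivalent baseline-adjusted Week 8 contrast from the repeated measures model. Keep the direction and level of the test, and report the adjusted difference with a confidence interval. Use the same model for the Week 12 between-group comparison listed in Section 4. Settle this before unblinding, so that the covariate cannot appear to have been chosen from the data.

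Align the endpoint wording in Sections 2.1 and 4 with the change or reduction in Sections 10.1.2, 10.2 and 10.5. With baseline as covariate, Week 8 score and change from baseline give the same treatment estimate, so this does not conflict with the model.

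The cost is wording in the analysis section, the synopsis and the objectives table. No new data or subjects are needed, and the sample size of 102 can stay.
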